Interview of patients showed that most patients would agree that HF-SMAs are helpful: *"I find it informational..different people have different ideas..last time I came in, one of the gentlemen that was having trouble with his ankles..socks a little too tight..then somebody says, then cut the top of the socks off..."* Medication reconciliation and adherence as well as diet counseling are two most frequently mentioned themes: *"Especially the medications, which I found out the hard way... 'cause I had stopped it...it got confusing to me, all the medications..."*; *"learn a lot about diet such as fat, salt and ice cream intake,... Send a cook-I don't know how to cook!"* We also learned that sometimes we give too much information to patients: *"...too much actually...I haven't read a book in like forty years..."* We also found out that at times we did not explain clearly why the patients are attending the HF SMAs: *"I don't remember it at all, so, that's why they ought to let people know what they're doing, exactly what they're there for, because I really wasn't sure why I was there.."* We also learned that patients within 1-2 weeks of hospital discharge are often too frail to want to attend SMAs and not eager to interact, so they often delay their appointment until 3-4 weeks out. These lessons helped us designed the current study to open the window of enrollment up to 12 weeks after their discharge.

Interview of physician stakeholders suggested that many physicians did not know about HF-SMAs or their patients attended HF-SMAs when referred by another provider. These observations taught us that communication with patient's physicians is important after the HF-SMAs for care coordination.

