#### 9. Quantitative Analytic Plan:

Aim 1: To compare between the intervention versus usual care arms in the change from baseline in KCCQ (Primary outcome) and EQ5D (secondary outcome) at 90 and 180 days. The analysis will be performed from an intention to treat principle. First, descriptive statistics (mean, standard deviation, median, inter-quartile range, and frequency distribution) will be calculated to summarize, at baseline, patients' demographic and comorbidities including previous hospitalizations, cardiac history (heart function and coronary disease), medical and health service utilization information (including medication possession ratio, HF self-care index, BNP levels, enrollment into HF clinics / programs, visits with primary care and cardiologists), and the primary outcome of interest (KCCQ, overall score) according to randomized arms. Log-transformation of variables and outcomes of interest will be performed to approximate normality when appropriate. Linear mixed-effects (LME) model will be utilized for the analysis of this aim, where the response variable is KCCQ, fixed effects include treatment group, time (0 = baseline, 1 = at 90 days, 2 = 180 days), treatment group by time interaction, and other important demographic variables identified in the descriptive analysis, and random effects include site-specific random intercept, subject-specific random intercept (nested within site) and subject-specific random slope of time. This modeling approach has been shown to provide an unbiased and efficient estimate of the longitudinal treatment effect in a variety of situations, such as in the presence of missing data, imbalance of the primary outcome at baseline, and covariance heterogeneity between treatment groups. In this way, we could compare the intervention effects at 90 days and whether residual effects exist at 180 days. The random site effect is used to model the clustering effect of patients in the same study site and random subject effects are used to model the variability in the subject-specific trajectory and the correlation of repeated measures within subject. Residual analysis will be conducted to examine the appropriateness of the functional forms of each fixed effect, and Information criteria (AIC, BIC) will be used to choose the correlation structure.

Secondary: Same modeling technique will be used to study EQ5D as the outcome instead of KCCQ.

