Sample Size and Power Considerations: The overall study sample will be 375 (225 patients from Phoenix VAMC and 150 patients from Providence VAMC). Statistical power for the aims 1 and 2 is estimated given these are the most relevant and the most restrictive in terms of power estimations. Under a conservative dropout rate of 15% for 180 days of follow-up for the main outcomes (Aims 1 and 2), we estimate the power with an effective sample size of 316 (15% less than the total sample) and a 2-sided significance level of 0.05 using nQUERY Advisor 7.0®. For aim 1, we assess the power to detect a clinically significant change in KCCQ of 5 points, assuming a baseline score of 63 (our preliminary studies), with a common standard deviation of 15 for the study arms, using a 2-sample t-test. For aim 2, we assess the power to detect a relevant decrease in rehospitalization or death risk of 25-30% at 180 days using a Cox Proportional Hazards model. Based on our preliminary data of 20,000 Veterans with ejection fraction <40% hospitalized with HF, their rehospitalization rates at 6 months is ~40%. Assuming similar event rates for rehospitalization or death, as shown in Table 2, we have good power to detect the proposed outcomes at very conservative estimates of effective sample size (n=158 in each arm, which is 85% of the total proposed recruitment target). Repeated measures at 90 and 180 days are also likely to add to the statistical power in Aim 1 to detect differences at the subgroup levels.

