**11. Limitations and potential shortfalls:** First, it is possible that secular trends such as an increase in the availability for co-interventions threaten our experimental design and cause underestimation of our treatment effects. We are using stratified randomization to balance current co-interventions and will track this carefully during the enrollment period. Adjusted analyses for imbalanced in exposure to co-interventions during follow-up will be performed when necessary and stratified analyses by co-interventions will also be explored as detailed in our analysis plan. In addition, it is likely that the effects of secular trends should be randomly distributed in a randomized controlled study, such that co-interventions should not have a differential effect. Second, our study duration is only 6 months. Based on our previous data on diabetes, the effect of SMAs on patient's outcomes are the highest while the patient is enrolled in the program and gradually declines after the stop of sessions unless booster sessions are planned. Given limitation of resources, we would like to test the short and mid-term effectiveness of the intervention first, prior to studying maintenance programs. Third, there is always a risk of not achieving the targets for patient recruitment. Fortunately, the project team is very experienced, and has had excellent track records in patient recruitment and retention in previous studies of similar characteristics. The use of 2 study sites will provide us with additional protection to achieve recruitment goals. Fourth, variation in effect size: It is possible that we found that the intervention may be effective in one site but not another, or in certain patient subgroups but the overall effect may not be large. This problem can arise due to distinct standards of usual care provided to patients and different settings of care. However, understanding these differences through this study will be important to know which settings and patients to target to derive the most benefits.

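### The stated random intercept and slope make KCCQ change equally variable in both 90-day intervals unless AIC/BIC moves to an unlisted structure; if the two differ, the day-90 standard error is wrong in an unknown direction

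*Combined protocol and SAP*

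**What the plan says.** All of this stands in the combined protocol and SAP, section 9 (Quantitative Analytic Plan), unless noted.

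- Random effects for KCCQ: "random effects include site-specific random intercept, subject-specific random intercept (nested within site) and subject-specific random slope of time". Their stated purpose: "random subject effects are used to model the variability in the subject-specific trajectory and the correlation of repeated measures within subject".
- Fixed effects include "time (0 = baseline, 1 = at 90 days, 2 = 180 days), treatment group by time interaction". The plan does not say whether time is categorical or linear.
- Aim of the model: "we could compare the intervention effects at 90 days and whether residual effects exist at 180 days". That needs a separate effect at each visit, so categorical visit is the reading that fits.
- Choice of covariance: "Information criteria (AIC, BIC) will be used to choose the correlation structure". No candidate structures are listed, and there is no rule for when the two criteria disagree.
- The robustness claimed for the model covers covariance that differs between treatment groups, not variance that differs between visits.
- The same model is reused for EQ-5D and for both Aim 3 outcomes.
- Power is calculated with an "effective sample size of 316 (15% less than the total sample) and a 2-sided significance level of 0.05". Table 2 gives it at 180 days only.

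**The concern.** A random intercept and slope is a four-parameter description of a 3x3 covariance matrix that has six free elements. One restriction it brings is that change must be equally variable in the two intervals. The intervals are not alike by design. Sessions are planned for about the first 8 weeks after randomization, while the second interval is mainly follow-up. Nothing in the plan justifies equal variances.

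Day 90 is one of the two time points named for the primary outcome and the visit closest to the planned end of the sessions. If the restriction is false, the two-sided 0.05 level does not hold there. The same would apply to EQ-5D, self-care and BNP.

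**Working it through.** **Inputs.** Time 0/1/2, the random effects, two-sided 0.05, 158 per arm and SD 15 come from section 9. The ratio r = Var(KCCQ180 − KCCQ90) / Var(KCCQ90 − KCCQ0) is not in the documents. It is an assumption, shown over a range.

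**1. The plan's own figure.** For a 5-point difference, SE = 15 × √(2/158) = 1.688. Then 5/1.688 = 2.963, and power = Φ(2.963 − 1.960) = 0.842 (0.840 with the noncentral t). Table 2 states .84, so it reproduces. It refers to day 180; the plan gives no standard error or power for day 90.

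**2. The restriction.** Let D22 be the slope variance and σ² the variance of independent residuals. Then

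- Var(Y90 − Y0) = D22 + 2σ²
- Var(Y180 − Y90) = D22 + 2σ²

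Compound-symmetric and AR(1) residuals change the residual term equally in both lines, so the equality stays.

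**3. What the fit returns.** Write L = (Y180 − Y0)/2 and Q = Y0 − 2·Y90 + Y180. Then Y90 − Y0 = L − Q/2 and Y180 − Y90 = L + Q/2. The model sets Cov(L, Q) = 0 but leaves Var(L) and Var(Q) free. With V1 and V2 the true early and late change variances, the fitted day-90 change variance is therefore Var(L) + Var(Q)/4 = (V1 + V2)/2. Hence

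- model SE / true SE at day 90 = √((1 + r)/2)
- type I error = 2 × [1 − Φ(1.96 × √((1 + r)/2))]

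Var(Y180 − Y0) = 4·Var(L) is not restricted, so the day-180 ratio is 1.000 with complete data. Numerical fits confirmed this.

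**4. Results.** The last column assumes an early-change SD of 15, which gives a true SE of 1.69.

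| r (late/early) | SE ratio | 1.96 × ratio | Type I error, day 90 | Model SE |
|---|---|---|---|---|
| 0.5 | 0.866 | 1.697 | 9.0% | 1.46 |
| 0.8 | 0.949 | 1.859 | 6.3% | 1.60 |
| 1 | 1.000 | 1.960 | 5.0% | 1.69 |
| 1.25 | 1.061 | 2.079 | 3.8% | 1.79 |
| 2 | 1.225 | 2.400 | 1.6% | 2.07 |

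Simulation (4,000 complete-data trials per setting, 158 per arm, two assumed correlations between early and late change) gave 9.5% and 9.8% at r = 0.5, and 5.6% and 5.7% at r = 0.8. An unstructured covariance gave 4.6% to 5.9% across all settings. Adding an AR(1) residual left the day-90 SE ratio at 0.864 to 0.866 for r = 0.5.

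**5. Can the selection step cure it?** Yes, with the right candidates.

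- *Visit-specific residual variances beside the random slope:* 3 + 3 = 6 parameters for 6 moments. With c01, c02 and c12 the covariances between visits, D12 = c02 − c01, D11 = 2·c01 − c02 and D22 = (c12 − D11 − 3·D12)/2; the three variances then give the residuals. For assumed equal variances and correlations (0–90 / 0–180 / 90–180) of .5/.45/.7, .5/.5/.75 and .4/.35/.7, the day-90 variance ratio rises from 0.80, 0.75 and 0.75 to 1.00, 1.00 and 0.98.
- *Unstructured covariance replacing the random effects:* at r = 0.5, AIC and BIC both chose it in nearly every simulated trial. At r = 0.67 (V1/V2 = 1.5), AIC chose it in 96–98% and BIC in 64–77%. At r = 0.8, the figures were 61–73% and 11–21%.
- *Independent, compound-symmetric or AR(1) only:* no cure, because all keep the equality.
- *A full unstructured residual matrix added to the random effects:* not estimable, with 3 + 6 = 9 parameters for 6 moments.

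**The case against.** The strongest reply is that the plan does not lock in the restriction. The AIC/BIC sentence can be read as allowing visit-specific residual variances, which keep the random slope and remove the equality. In 1,000 simulated trials under each of the first two covariances in step 5, that model gave 5.2% and 5.7% type I error, against 8.7% and 9.0% with equal residual variances. AIC chose it in at least 99.9% of trials, and BIC in 94% and 100%. This stands: a reader might infer that the plan forces the error, and it does not. What remains is that the candidates are unlisted, common stationary choices leave the restriction in place, and BIC often misses a moderate gap even with an unstructured candidate.

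A reader might also infer from the plan that early change is the more variable, so that the error is inflation. The documents do not support this.

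- Section 11 (Limitations) says that SMA effects "are the highest while the patient is enrolled in the program and gradually declines after the stop of sessions". That concerns the mean effect, in diabetes.
- The Providence pilot notes that "patients within 1-2 weeks of hospital discharge are often too frail to want to attend SMAs", and uses this to justify enrollment up to 12 weeks after discharge. Many baselines may therefore fall after early recovery.
- The ±30-day visit windows in section 8 allow 60 to 120 days for the first interval but 30 to 150 for the second. That could make late change the more variable.
- Type I error is computed under no treatment effect, so differing response to the sessions cannot add early variance there.

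Finally, the issue needs categorical visit. With linear time there is no separate day-90 effect to test, though the plan says that it wants one.

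**Conclusion.** The concern holds as a conditional one. The stated random effects, with equal-variance or stationary residuals and categorical visit, equate the two change variances. If they differ in truth, the day-90 standard error is wrong by the factor √((1 + r)/2). Over an assumed r of 0.5 to 1.25, type I error runs from about 9.0% down to 3.8%. The documents do not fix r, so neither direction nor size can be stated.

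It would be too strong to say that the primary analysis is invalid. The powered day-180 contrast is unaffected with complete data. The effect of the planned-for 15% dropout on either contrast was not quantified. This is a cheap improvement to an under-specified covariance at one of the two primary time points, not a demonstrated error in the result.

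**What to change.** In section 9, Aim 1, replace the subject random intercept and slope, and the AIC/BIC choice, with:

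- visit as a categorical factor with its treatment interaction;
- a pre-specified unstructured 3x3 within-subject covariance over baseline, day 90 and day 180;
- Kenward-Roger degrees of freedom;
- one named fallback structure, used only if the model does not converge.

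Apply the same wording to EQ-5D and to the Aim 3 outcomes. A near-equivalent that stays closer to the present text is to keep the random slope and pre-specify visit-specific residual variances.

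The cost is SAP wording and two extra variance parameters (6 instead of 4), which is little with 375 patients. In return, the day-90 error rate holds whichever way the variances differ, and a data-driven choice leaves the primary analysis.

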Kansas City Cardiomyopathy Questionnaire (KCCQ)(Appendix): is a 23 item instrument validated in stable and decompensated HF patients with preserved or reduced ejection fraction. The questionnaire takes 4-6 minutes to complete, and reflects disease-specific health status over the prior two weeks. The domains of KCCQ are physical limitation, symptoms, self-efficacy, social limitation, and quality of life. The domains of the KCCQ have a high internal consistency with a Cronbach's alpha of 0.95 for the Overall Summary Score and  $\geq 0.62$  for all individual scales. The KCCQ has a significantly higher responsiveness to changes in health status than the Minnesota Living with Heart Failure Questionnaire and the SF-36. The overall summary score is 0-100 where higher score is better. The minimal clinically important change in survey score is 5 points, with a 10- and 20-point change reflecting moderate and large clinical changes, respectively. In the Eplerenone Post-AMI Heart Failure Efficacy and Survival Trial (EPHESUS), each 5-point decline in KCCQ Overall Summary Score on serial assessments was associated with a hazard ratio of 1.11 (95% CI, 1.05-1.17) for subsequent cardiovascular death or hospitalization. Preliminary data from Phoenix VA found a median Summary Score of  $52.4 \pm 27.8$  (n =32) in HF-SMA participants indicating fair/poor health status.

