HF Self-Care - The HF Self-care Index (v.6)(Appendix): is a 22-item self-administered instrument composed of 3 scales: self-care maintenance, management, and confidence. It addresses diet, exercise, medication use, when to call the health provider, keeping doctor's appointments, weight monitoring, and recognition of change in health status or symptoms. Each scale is scored separately and has a range of 0-100. A score of  $\geq 70$  on each scale is considered adequate self-care, though benefit occurs at even lower levels. A score change of half standard deviation ( $\approx 8$  points) is considered a clinically relevant change. Pilot data from Phoenix VA showed low self-care scores in HF patients ( $64.9 \pm 19.9$ ) at baseline.

Plasma BNP levels: is a hormone released mainly by the heart in response to excessive stretching of heart muscle cells in cases such as HF. It is a test that is already being collected routinely in the clinical setting for HF patients. A cut-off of  $>100$  pg/mL in patients with new-onset dyspnea is suggestive of acute HF. It can also be used in outpatients after HF discharge to monitor for clinical deterioration and is highly predictive of death or rehospitalization, with a hazard ratio per unit increase of ln BNP of 1.84 (95% CI: 1.42 to 2.39). BNP provides clinicians with an objective and simple measure of the loading conditions of the heart.

Aim 4: Pre-implementation assessment.

1) Patients: We will conduct interviews of 20-25 patients in each study site who have undergone HF-SMA (with their caregivers if willing). Interviews will attend to patient (and caregiver) satisfaction and feedback on refinements for continuous quality improvement and determine, in what ways, the HF-SMA helped or did not help them feel better and/or avoid hospitalizations. We will strive for a maximum variation sampling of patients based on sociodemographic characteristics (age, women and minorities), number of co-existing conditions, social support and engagement during the sessions to achieve maximal thematic heterogeneity.

2) Stakeholders – Providers and administrators: We will interview ~10 physician stakeholders at each site, which will include primary care providers or cardiologists and one physician administrator (e.g. Chief of Cardiology, Medicine or Primary Care). We will purposefully select physicians who oversee HF patients who

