**Medical co-morbidities and cardiac history:** based on the Charlson Co-morbidity index, this data will be collected through chart abstraction by our research assistants at baseline and confirm it with patient and caregiver. The Charlson Co-morbidity index is a weighted index that takes into account the number and the seriousness of comorbid disease. The index is well validated for its ability to predict risk of death from co-morbidities at 1-year and 10-year follow-up periods. We will also obtain cardiac testing data including echocardiography, cardiac catheterization, and stress test data through review of medical records. Non-VA sources will be contacted if indicated to track non-VA care (Table 1 of data collection below)

Table 1. Timeline of Data Collection	Baseline	90 days	180 days	Data Source
Charlson Comorbidity Index	X			Patient, family and chart
Caregivers / Demographics	X			Patient, family and chart
Echocardiography, cardiac testings	X			Patient and chart
KCCQ, EQ-5D	X	X	X	Patient
HF Self-care Index, PACIC, PHQ-8, BNP	X	X	X	Patient
Patient (± caregiver) satisfaction	Ongoing			Interview
Provider perception	Ongoing			Interview
Hospital admission or death	Ongoing			Patient, family and chart
HF clinics / programs	Ongoing			Patient, family and chart
Outpatient physician and ER visits	Ongoing			Patient, family and chart

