Aim 2: To compare between the intervention versus usual care arms in hospitalization or death at 90 and 180 days after the randomization. For this analysis Cox proportional hazards model will be utilized where the event is a composite outcome that represents either hospitalization or death. Any patient who does not experience the event by 180 days will be denoted as censored. The main exposure is treatment group and other covariates include patient demographic and comorbidity information as described above. We will examine the differences in outcome at both 90 and 180 days. The appropriateness of the proportional hazards assumption will be examined and any violation of the assumption will be addressed. The appropriateness of the functional forms of each covariate will be assessed through residual analysis.

Aim 3: To compare between the intervention versus usual care arms in the change from baseline in patient's (a) HF Self Care index and (b) BNP levels, we will use the same linear mixed-effects modeling approach as described in Aim 1.

Subgroup and Sensitivity Analyses: In order to understand potential heterogeneity of treatment effects, stratified analyses will be conducted by our randomization stratifiers such as co-interventions or not, ejection fraction ( $\geq 40\%$  &  $< 40\%$ ), and hospitalizations in the previous 6 months ( $> 2$  &  $\leq 2$ ). Given that baseline KCCQ scores, HF self-care behavior, comorbidity burden, depression symptoms and caregiver support could potentially change the outcome of HF, we will conduct test for multiplicative interaction between the condition of interest (e.g. depression with PHQ-8  $\geq 10$  vs.  $< 10$ ) and the study arm allocation (intervention vs. usual care arm) on the patient outcomes of interest described in Aims 1 and 2. *If any these interaction terms are significant at an alpha level of 0.05 or less*, subgroup analyses will be conducted (e.g. number of comorbidities below and above the median, baseline KCCQ scores above and below the median, and by presence or absence of significant depression symptoms or caregiver support) depending on the feasibility by sample size. Sensitivity analyses will be performed by study site to determine the impact of setting in our study findings and potential variation of findings.

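### The Aim 2 Cox model does not commit to baseline ln BNP or baseline KCCQ as covariates, which gives up a few points of power although both are measured at baseline

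*Combined protocol and SAP*

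**What the plan says.** Section 9 (Quantitative Analytic Plan), Aim 2, specifies a Cox model in which "the event is a composite outcome that represents either hospitalization or death", with censoring at 180 days. Its covariate sentence is: "The main exposure is treatment group and other covariates include patient demographic and comorbidity information as described above".

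The text referred back to is the Aim 1 paragraph of the same section, a long list of baseline variables to be summarized by arm. There BNP appears under "medical and health service utilization information (including medication possession ratio, HF self-care index, BNP levels", and KCCQ comes separately at the end: "and the primary outcome of interest (KCCQ, overall score) according to randomized arms". The list does not say which variables enter the Cox model.

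Other relevant text:

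- **Plasma BNP levels (section 8):** BNP is described as strongly predictive of death or rehospitalization, "with a hazard ratio per unit increase of ln BNP of 1.84 (95% CI: 1.42 to 2.39").
- **KCCQ (section 8):** "each 5-point decline in KCCQ Overall Summary Score on serial assessments was associated with a hazard ratio of 1.11 (95% CI, 1.05-1.17"), for later cardiovascular death or hospitalization.
- **Background, and Subgroup and Sensitivity Analyses:** health status is called an independent predictor of death and hospitalization, and baseline KCCQ is listed among factors that could alter outcome. Neither place gives a figure.
- **Table 1:** KCCQ is scheduled at baseline, as is the row "HF Self-care Index, PACIC, PHQ-8, BNP".
- **Section 5 (Randomization and retention):** stratification is by site, co-intervention, hospitalizations in the last 6 months and ejection fraction. The Aim 2 sentence does not name these stratifiers.
- **Missing Data Issues:** when fewer than 5% of observations have missing values, the variables with missing values are removed.

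**The concern.** In a Cox model, leaving out a strong baseline predictor has a cost even when randomization is perfect: the treatment hazard ratio moves toward 1 and the test loses power. Aim 2 is secondary, but it is one of the two aims for which the plan computes power. If the analyst adjusts only for demographics and comorbidity, information already in the database goes unused. If the analyst decides later whether to add BNP or KCCQ, the choice may be made with the outcome data in view. The missing-data rule adds a further risk: read literally, a handful of missing BNP draws would remove BNP even if the analyst had meant to include it.

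**Working it through.** **1. What the text commits to.** The Aim 2 sentence names demographics and comorbidity. The list it points to has BNP under medical and utilization information and KCCQ as the primary outcome. A loose reading could admit BNP; no reading requires it. Baseline KCCQ is planned for Aim 2 only in interaction and subgroup tests.

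**2. The plan's own power figure.** Inputs from Sample Size and Power Considerations: 158 per arm, two-sided alpha 0.05, about 40% events at 6 months. For a hazard ratio (HR) of 0.73, Table 2 states power 0.80.

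- Events = 158 × [0.40 + (1 − 0.60^0.73)] = 158 × (0.40 + 0.311) = 112.4
- Power = Φ(√112.4 / 2 × |ln 0.73| − 1.96) = Φ(5.30 × 0.3147 − 1.96) = Φ(−0.29) = 0.385
- With all 316 patients counted as events: Φ(8.89 × 0.3147 − 1.96) = Φ(0.84) = 0.80

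Table 2 is therefore reproduced only if every patient is an event. The covariate question has to be judged from about 0.38, not 0.80.

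**3. Prognostic strength.**

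- ln BNP: ln 1.84 = 0.610 per ln unit. The SD of ln BNP is assumed at 0.7, 1.0 or 1.3, giving a log-hazard SD of 0.43, 0.61 or 0.79.
- KCCQ: ln 1.11 / 5 = 0.0209 per point. With the planning SD of 15 this is 0.31. Applying it to the baseline level is an assumption, because the cited figure is for decline.

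**4. Simulation against a treatment-only model.** Exponential event times, 158 per arm, 40% usual-care events by day 180, conditional HR 0.73, 8,000 runs per row, about 114 events. The two cited hazard ratios are assumed to hold jointly. KCCQ SD is 15 (planning) or 27.8 (Phoenix pilot). Correlation is between ln BNP and worse KCCQ.

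| SD ln BNP | SD KCCQ | Correlation | HR without both | Power without both | Power with both |
|---|---|---|---|---|---|
| 0.7 | 15 | 0 | 0.743 | 0.345 | 0.384 |
| 1.0 | 15 | 0 | 0.750 | 0.327 | 0.387 |
| 1.0 | 15 | 0.3 | 0.758 | 0.307 | 0.380 |
| 1.0 | 27.8 | 0 | 0.764 | 0.290 | 0.378 |
| 1.3 | 27.8 | 0.3 | 0.782 | 0.257 | 0.384 |

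The gain is about 4 to 13 points. When only ln BNP is prognostic (SD 1.0), adjusting for it raises power from 0.336 to 0.381; when only KCCQ is (SD 15), from 0.368 to 0.382. With no treatment effect, the rejection rate is about 0.05 with or without the covariates. If 0.73 is instead taken as the unadjusted hazard ratio, the middle case goes from 0.39 to 0.46.

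**5. Simulation against a model that already adjusts.** The plan's model is not treatment-only, so the gains in step 4 are upper bounds. A comorbidity score (assumed log HR 0.3 per SD) was put in both models.

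- Score correlated 0.3 with the other predictors, ln BNP SD 0.7 to 1.3: ln BNP alone gains about 2 to 9 points; both covariates gain about 3 to 11.
- ln BNP SD 1.0, KCCQ SD 15, adding both: at HR 0.73, power rises from 0.31 to 0.38 (score correlation 0.3) or 0.34 to 0.37 (0.5). At HR 0.69 it rises from 0.41 to 0.50 or 0.44 to 0.50.
- One existing covariate correlated 0.5 to 0.7 with ln BNP, HR 0.73: ln BNP alone adds about 3 to 4 points at SD 0.7 or 1.0, and 5 to 6 at SD 1.3.

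**The case against.** The strongest reply is that nothing has been left out. The covariate sentence is open, and the list it points to contains BNP and KCCQ. That stands against a reader who infers that the plan excludes them: the documents show an uncommitted covariate set, not an exclusion.

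Four other replies also have force:

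- **BNP and KCCQ are not the only predictors cited.** The Charlson index, self-care, depression and caregiver support also appear. The case for BNP is that it has a figure for nearly the same endpoint; KCCQ has only general support.
- **The KCCQ figure does not measure what is needed.** It was observed "on serial assessments was associated with a hazard ratio of 1.11 (95% CI, 1.05-1.17) for subsequent cardiovascular death or hospitalization", so it concerns change over time and a cardiovascular composite. The gains that include KCCQ rest on that borrowed value.
- **The shift in the hazard ratio is not bias.** It is the difference between a marginal and a conditional hazard ratio. A reader might infer that the analysis without these covariates is wrong, but its type I error is correct.
- **Randomization already balances part of the severity,** through ejection fraction and prior hospitalizations.

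These points limit the claim but do not remove it. A gain remains when a comorbidity score is already in the model, and nothing in the plan secures it.

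**Conclusion.** The point holds as a gap in commitment with a modest cost in efficiency. The Aim 2 model does not commit to baseline ln BNP or baseline KCCQ. The test without them is valid but less powerful, and its hazard ratio lies nearer 1. The expected gain is about 2 to 9 points of power from ln BNP and about 3 to 11 from both. This rests on an assumed ln BNP SD of 0.7 to 1.3, an assumed comorbidity score (log HR 0.3 per SD, correlation 0.3), and the cited hazard ratios applying to baseline values in this population. Stronger overlap with existing covariates shrinks it.

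It would be wrong to infer that the change rescues Aim 2. Power at HR 0.73 with 40% events is about 0.38, against the 0.80 in Table 2, and adding both covariates does not bring it near 0.80. That discrepancy needs its own correction.

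**What to change.** In section 9, Aim 2, state that:

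- the main Cox model will include treatment group, baseline ln(BNP) and baseline KCCQ overall summary score (both continuous), the demographic and comorbidity covariates, and the randomization stratifiers of section 5;
- missing baseline covariate values will be imputed without using treatment arm, and the Missing Data Issues rule of removing variables with missing values does not apply to them;
- the hazard ratio is conditional on these covariates, and the unadjusted hazard ratio and Kaplan-Meier curves will be reported alongside.

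The cost is a short addition to the Aim 2 text and an exception in the missing-data text, with no new data, visits or patients. The downside is a few more model terms on about 110 events, and a main estimate that must be described as conditional.
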